The primary safety analyses will focus on the 24-week time period during BDQ treatment and will include only participants whose total exposure to BDQ ~~has been~~ was at the final ~~BDQ dose~~ ~~recommended~~ **implemented dose** for their cohort for the protocol-specified period of BDQ administration. Participants who have been removed from treatment, or who have had their doses reduced as part of cohort management due to toxicities, will be included and treated as safety failures in the primary safety analysis (note that such participants may have to be excluded from any

secondary analyses which require complete follow-up at the optimal dose). Participants whose doses have been adjusted on the basis of PK results will be excluded from these primary analyses, regardless if the participant initiated BDQ at the final ~~recommended~~ **implemented** dose, and sensitivity analyses performed in an attempt to determine whether the exclusion of these participants creates a selection bias which impacts upon any results. These primary analyses will be performed after the last participant of the last cohort has completed the study drug regimen over the 24-week dosing period.

2. *Section 9.6.1, Primary Safety Analyses, fourth paragraph:*

In addition, if possible, a primary evaluation of safety across the 24 weeks of study treatment will be performed on the data from participants who have been started at the final recommended dose for a given cohort and have remained on that dose for the 24-week period or have left the study or had a dose modification due to safety failure prior to 24 weeks of exposure (in which case the participant will be analyzed as a failure). Note that such an analysis may not be possible, since the PK modeling procedure which will determine the final recommended dose will not guarantee that an adequate number of participants be on that dose. However, secondary safety analyses will include all safety data collected from first participant exposure to the end of the study, with results broken down by dose. This will include data representing the final **implemented** dose for each cohort, as well as data gathered during the dose finding stage, which may represent exposure to doses which have failed.

3. *Section 9.6.2.1, Safety, first paragraph:*

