1.2 Version History

The original version of the SAP was updated (V 1.1) to account for Letter of Amendment (LoA) #2, dated 28 February 2019, and LoA #3, dated 17 October 2019, for Protocol Version 1.0, dated 3 March 2016, and included updates to the Bedaquiline (BDQ) dosing regimen for all cohorts, as was determined by population PK modeling performed based on PK data for the first 12 evaluable participants in Cohort 1 (consistent with protocol Sections 3.2 and 10.2.3). In addition, this version also accounts for Clarification Memorandum (CM) #6, dated 1 April 2020, which provided guidance to sites for conducting study visits and procedures during the COVID-19 pandemic and recommended prioritization for conduct of clinically and scientifically important evaluations.

The next version 1.2 accounted for LoA # 4 dated 27 June 2022, which incorporated contents of protocol CM #6 that provided operational flexibility for conducting study visits and procedures when needed and to prioritize the conduct of clinically and scientifically important evaluations when possible. Consistent with the instructions provided in CM #6, implementation of this LoA is expected to be time-limited in relation to the COVID-19 pandemic.

Version 2 reflected updates based on Protocol Version 2.0, dated 21 September 2022, with CM #1, dated 29 March 2023.

This current version just notes the version change based on LoA #1 dated 2 May 2023 to Protocol Version 2.0/

2 Study Overview

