4.1 General Considerations

The primary safety analyses will focus on the 24-week time period during BDQ treatment and will include only participants whose total exposure to BDQ was at the final implemented dose for their cohort for the protocol-specified period of BDQ administration. Participants who have been removed from treatment, or who have had their doses reduced as part of cohort management due to toxicities, will be included and treated as safety failures in the primary safety analysis (note that such participants may have to be excluded from any secondary analyses which require complete follow-up at the optimal dose). Participants whose doses have been adjusted on the basis of PK results will be excluded from the primary safety analyses, regardless if the participant initiated BDQ at the final implemented dose, and sensitivity analyses performed in an attempt to determine whether the exclusion of these participants creates a selection bias which impacts upon any results. These primary analyses will be performed after the last participant of the last cohort has completed the study drug regimen over the 24-week dosing period.

Each participant's safety data will be summarized as: (1) the most severe grade of AEs, and (2) the most severe grade of AEs assessed to be at least possibly related to study treatment. Frequency distributions of these safety outcomes will be presented in aggregate and will be broken down by age cohort. Listings of all \geq grade 3 events will be provided.

The proportions of participants experiencing \geq grade 3 AEs will be presented in aggregate and broken down by age cohort, with these proportions bounded by exact 95% CIs. If sample size allows, frequencies and proportions will be presented by weight band; similarly, by HIV status, broken down by age cohort and/or in aggregate. Similar analyses will present the proportions of participants exhibiting \geq grade 3 events which have been assessed to be at least possibly related to study drug, again bounded by exact 95% CIs. Tabulations will also be presented to summarize all AEs, as well as all AEs which have resulted in treatment discontinuation. Summary statistics of QT values at each time point performed will also be presented. Additionally, listings of participants who experience unstable dysrhythmias requiring hospitalization and treatment will be presented.

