In addition, if possible, a primary evaluation of safety across the 24 weeks of study treatment will be performed on the data from participants who initiated the final recommended BDQ dose for a given cohort and remained on that dose for the 24-week period or have left the study or had a dose modification due to safety failure prior to 24 weeks of exposure (in which case the participant will be analyzed as a failure). Note that such an analysis may not be possible, since the PK modeling procedure which will determine the final recommended dose will not guarantee that any participant, or an adequate number of participants, be on that dose. However, secondary safety analyses will include all safety data collected from first participant exposure to the end of the study, with results broken down by dose. This will include data representing the final implemented dose for each cohort, as well as data gathered during the dose finding stage, which may represent exposure to doses which have failed.

Given that the modest sample sizes within cohorts will provide limited power for statistical tests of differences across age cohorts, only very large apparent effects would be statistically significant. Interpretation of differences across cohorts will depend upon whether these differences are great enough to be considered to be clinically significant. If no such differences are observed, then the clearest interpretation of the findings will come from the aggregated data, where analyses will have the greatest statistical precision. However, if results vary across cohorts to a clinically important extent, interpretation of results should consider the age differences and potential treatment differences represented by this stratification factor.

The proportions of participants meeting each of the endpoints which would trigger an *ad hoc* SMC review will be presented descriptively. Details concerning the analyses will be included in a separate analysis plan.

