4.3 Safety Analysis Sets

The primary analysis set consists of all participants whose total exposure to the study drug BDQ was at the final implemented dose for their cohort for the protocol-specified period of BDQ administration. Participants who discontinued study drug due to toxicities will be considered a safety failure for this primary safety outcome measure* and will be considered an intercurrent event for the other primary safety outcome measures. Those who have had their doses adjusted as part of cohort management due to toxicities will be treated as safety failures* in the primary safety analysis. Participants who have been removed from study treatment for any reason (other than toxicity*) will be considered as having experienced an intercurrent event and will be included in the primary analysis dataset. These participants will be analyzed with the approach that those who experienced a primary safety outcome measure while on study drug will be considered as safety failure for that outcome measure. Those who were off study before the Week 24 visit due to reasons other than death will be included and will not be considered as a safety failure unless this was experienced before they were off study and while on study drug. The following sensitivity analyses will also be performed for participants who were off study before the Week 24 visit:

- The participant will be treated as safety failure (worst case)
- The participant will be excluded from the safety analysis set

Supplementary safety analysis dataset: All participants who were exposed to the study drug BDQ, including those who did not receive the final implemented dose evaluated in the study, as well as those whose dosing was amended based on PK considerations. The analysis approach will follow the same approach as that for the primary analysis set.

*Note that this refers to the relevant primary safety outcome (for example if the toxicity is “AEs of at least Grade 3 severity assessed by the Core Team to be at least possibly

related to study drug" then the participant will be considered a safety failure for this particular outcome measure only)

5 Report Contents

Detailed descriptions of the content of each of the following sections are given in the AIP.

1. Accrual
 - Screening (will be summarized in text only)
 - Number screened
 - Screening failure reasons
 - Enrollment
 - Number enrolled
2. Protocol deviations

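### Does the SAP need to define the sensitivity analysis promised for participants excluded after PK-driven dose changes?

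*SAP*

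**What the plan says.** Under SAP 4.1, a participant whose dose was changed because of PK results "will be excluded from the primary safety analyses, regardless if the participant initiated BDQ at the final implemented dose". The protocol's Clarification Memorandum #1, in its revision of section 9.6.1, has the same rule: such participants "will be excluded from these primary analyses, regardless if the participant initiated BDQ at the final" implemented dose. Both texts then promise "sensitivity analyses performed in an attempt to determine whether the exclusion of these participants creates a selection bias which impacts upon any results". Neither states who enters those analyses or what is compared with what.

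SAP 4.3 spells out two sensitivity analyses, worst case and exclusion, but for another group: "The following sensitivity analyses will also be performed for participants who were off study before the Week 24 visit". It also defines a supplementary set of everyone exposed to bedaquiline, "including those who did not receive the final implemented dose evaluated in the study", together with those whose dosing was amended for PK reasons. That set is analysed in the same way as the primary set.

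Two further outputs touch the point. The secondary safety analyses in SAP 4.1 are split by dose and take in "data gathered during the dose finding stage, which may represent exposure to doses which have failed". Protocol section 9.6.2.1, as revised in the memorandum, adds descriptive and exposure-related analyses of participants with individual adjustments or on other doses.

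**The concern.** The plan names a possible selection bias, commits to examining it, and then does not attach the commitment to a set. Someone looking for the check in SAP 4.3 would probably settle on the supplementary set, which differs from the primary set in two ways at once: it restores the PK-adjusted participants and it adds people treated at other doses. A gap between the two results could then come from dose, and a real selection effect could be hidden by dose.

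Other-dose participants may well exist. SAP 1.2 records "updates to the Bedaquiline (BDQ) dosing regimen for all cohorts, as was determined by population PK modeling", the modelling being "based on PK data for the first 12 evaluable participants in Cohort 1", and that cohort enrols at most 24. The study is open-label, and SAP 2.4.1 notes that all planned interim PK and safety analyses are complete, so an undefined check could be settled with data in view. What is at stake is how well readers can judge whether the primary safety proportions represent everyone who started on the final implemented dose.

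**Working it through.** The plan gives no figure to reproduce here: neither document counts PK-adjusted or other-dose participants. For scale, the planned totals are 3 × 18 = 54 evaluable and 24 + 30 + 30 = 84 enrolled at most.

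**1. Who is in which analysis**

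| Analysis | PK-adjusted | Never at implemented dose | Period |
|---|---|---|---|
| Primary set (SAP 4.1, 4.3) | out | out | 24 weeks |
| Two sensitivity analyses (SAP 4.3) | not addressed | not addressed | 24 weeks |
| Supplementary set (SAP 4.3) | in | in | as primary |
| By-dose secondary (SAP 4.1) | in | in, split by dose | to end of study |
| Descriptive (protocol 9.6.2.1) | in | in | not stated |

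No row is exactly the primary set plus the PK-adjusted participants. That set does, however, lie wholly inside the supplementary set.

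**2. Event rule.** SAP 3.1 evaluates the primary outcomes through Week 24, and SAP 4.3 counts events occurring on study drug. A PK-driven dose change does not by itself take a participant off bedaquiline. The inherited approach therefore counts events through Week 24. Stopping the count at the dose change appears nowhere in the text.

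**3. Can the supplementary set alone isolate selection?** Let n and E be participants and events, with P for the primary set, A for PK-adjusted and O for other-dose participants.

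- Primary: E_P / n_P
- Add-back: (E_P + E_A) / (n_P + n_A)
- Supplementary: (E_P + E_A + E_O) / (n_P + n_A + n_O)

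Assumed counts: n_P = 36, E_P = 6, n_A = 6, n_O = 12, E_A + E_O = 4. Intervals are exact 95%.

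- Primary 6/36 = 16.7% (6.4 to 32.8)
- Supplementary 10/54 = 18.5% (9.3 to 31.4), wherever the 4 events fall
- Add-back with E_A = 0: 6/42 = 14.3% (5.4 to 28.5)
- Add-back with E_A = 2: 8/42 = 19.0% (8.6 to 34.1)
- Add-back with E_A = 4: 10/42 = 23.8% (12.1 to 39.5)

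One supplementary result thus fits add-back results on either side of the primary one, 4/42 = 9.5 points apart.

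A second example uses the Cohort 1 maximum of 24; everything else is assumed. Take 12 on superseded doses at 10% risk and 12 who started on the implemented dose at 20%, 2 of them adjusted (f = 2/12), with risk ratio k for adjusted against the rest.

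- Primary = 0.20 / (1 − f + f·k); supplementary = (12 × 0.10 + 12 × 0.20) / 24 = 15.0%
- k = 1: primary 20.0%, a 5.0-point gap without selection bias
- k = 3: primary 0.20 / 1.3333 = 15.0%, no gap despite a 5.0-point bias

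**4. When the difficulty disappears.** If n_O = 0, the supplementary formula becomes the add-back formula. If n_A = 0, the add-back equals the primary result. Both groups must exist for the supplementary set to mislead. With k = 1, and 0, 6 or 12 of 24 on superseded doses, the gap from dose mix alone is 0, 2.5 or 5.0 points.

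**5. Which participants to add back.** SAP 4.1 refers to everyone it excludes for PK adjustment, whether or not they started on the implemented dose. Invented data: 10 unadjusted starters with 1 event, 2 adjusted starters with 2, 4 switched from a superseded dose with 2, and 8 others with 0.

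- Primary: 1/10 = 10.0% (0.3 to 44.5)
- Starters added back: 3/12 = 25.0% (5.5 to 57.2)
- All PK-adjusted added back: 5/16 = 31.3% (11.0 to 58.7)
- Supplementary: 5/24 = 20.8% (7.1 to 42.2)

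The point estimates differ; the intervals overlap widely.

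**The case for a change.** The strongest argument for a change is that SAP 4.3 defines its other sensitivity analyses itself, so silence on this one looks like an omission rather than a deferral to the Analysis Implementation Plan. With interim data already reviewed in an open-label study, an unspecified check is open to later choice, and a sentence would cost almost nothing.

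Part of this stands. The link between the promise in 4.1 and a named set is missing. Whether to restore all PK-adjusted participants or only those who started on the implemented dose is left open. The supplementary set would be a poor substitute if both groups exist.

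The rest is weaker. The adjusted participants do have a set that contains them and an event rule by reference. Nothing in the plan designates the supplementary set as the selection-bias check, so the misleading comparison is one the analyst would have to choose. The by-dose and descriptive outputs, with the listings of grade 3 or higher events, would help show whether adjusted participants drive a difference. Table outlines and coding are assigned to the Analysis Implementation Plan, which is not available here; it may settle the point, though that cannot be confirmed. Any freedom that remains concerns a descriptive check in a single-arm study, not the primary set.

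**Conclusion.** This is missing detail of a kind that analysts fill sensibly, and no change to the plan is called for. The question posed in SAP 4.1 largely dictates its answer: restore the excluded participants to the primary set, count events through Week 24, and compare with the primary proportions using the exact intervals already planned. Participants who started on another dose can be identified separately in that report. This needs no new data, because the supplementary set already holds everyone required.

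No effect on any result has been shown. The 9.5-point and 5.0-point differences rest on assumed counts and risks; the only documented number among them is the Cohort 1 maximum of 24. The number of participants adjusted after starting on the implemented dose is not given and may be zero. SAP 1.2 makes superseded-dose participants plausible but does not say how many there were. The conclusion assumes that the team reads the promise as written and does not present the supplementary set, unqualified, as its test of selection bias.

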4.2 Analysis Approaches

This section contains the details of the analyses for:

- Interim and full cohort accrual safety reports [NOTE: At the time of finalization of this document, all planned interim PK and safety analyses for all cohorts have been completed]
- SMC Reports
- SDAC final reports

Summary tables will be generated by cohort and aggregated.

The interim and full cohort accrual safety reports will be prepared for the Core Team and will include Participant and Study Status and Safety Summary tables (these may be shared with the SMC).

The SMC reports will include information concerning Screening and Entry, Participant and Study Status, Baseline Characteristics, TB Treatment Outcome (if data are available), Safety summary tables, HIV-1 RNA and CD4 summary statistics, Data Completeness, and Protocol deviations Summary. Unless otherwise noted, the SDAC final reports will contain all summary tables.

Additional participant listings, not mentioned in this plan, but which may be necessary in writing up the SDAC final report, will be generated and will be used internally at SDAC. Highlights of these listings will be included in the SDAC final report. These participant listings will be provided to the manuscript writing team. The manuscript writing team, which is a subset of the protocol team, will be identified by the protocol team.

The analysis of the PK data will be performed by the protocol pharmacometrists and, thus, details of this analysis are not included in this document.

Validation requirements as per SDAC SOPs will be as follows:

- a. All dataset creation programs will be validated with double coding for the primary and secondary safety endpoints.
- b. All study-specific formats will be validated.
- c. Validation of analysis programs is specified in the subsections below.

For all analyses, the relative weeks of visit date/specimen date/onset date/other dates (“Assessment Window”) will be calculated using the following guidelines:

NOTE: Protocol Appendix XII provides site guidance for conducting study visits and procedures during operational disruptions due to the COVID-19 pandemic.

Study Day of Assessment	Assessment Window	Target Study Day of Window
0 to 1	Week 0	0
2 to 10	Week 1	7
11 to 20	Week 2	13
21 to 35	Week 4	28

36 to 49	Week 6	42
50 to 69	Week 8	56
70 to 98	Week 12	84
99 to 126	Week 16	112
127 to 160	Week 20	140
161 to 195	Week 24	168
196 to 252	Week 32	224
253 to 308	Week 40	280
309 to 364	Week 48	336
365 to 462	Week 60	420
463 to 546	Week 72	504
547 to 714	Week 96/End of Study visit	672
(Study day of last dose + 14)	Early Discontinuation	Study day of last dose + 1

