2.1 Study Design

This is a Phase I/II, open-label, single arm study to evaluate the PK, safety, and tolerability of BDQ given in combination with an individualized rifampin-resistant tuberculosis (RR-TB) therapy in infants, children, and adolescents with RR-TB disease, living with or without HIV.

Sample Size: Up to 84 participants total (24 for Cohort 1; 30 for Cohorts 2; 30 for Cohort 3) to achieve 54 evaluable participants (18 per age cohort):

Cohort 1: Age \geq 6 to < 18 years

Cohort 2: Age \geq 2 to < 6 years

Cohort 3: Age \geq 0 to < 2 years

Study Treatment and Duration: BDQ given as part of an individualized RR-TB treatment regimen for 24 weeks. For participants living with HIV, BDQ will be given in combination with an acceptable antiretroviral (ARV) therapy regimen initiated at least two weeks prior to enrollment.

Cohort	Age and Weight	BDQ Dosing
Cohort 1 up to 24 participants to achieve 18 evaluable (approximately nine in each weight band)	≥ 6 to < 18 years ≥ 30 kg	Participants ≥ 30 kg: 400 mg once per day through the intensive PK sampling visit*, then 200 mg three times per week on Monday, Wednesday, and Friday through the Week 24 visit
	≥ 6 to < 18 years ≥ 15 to < 30 kg	
Cohort 2 up to 30 participants to achieve 18 evaluable	≥ 2 to < 6 years > 7 kg	Participants > 7 to < 30 kg 200 mg once per day through the intensive PK sampling visit*, then 100 mg three times per week on Monday, Wednesday, and Friday through the Week 24 visit
Cohort 3 up to 30 participants to achieve 18 evaluable	≥ 0 to < 2 years ≥ 3 kg	Participants ≥ 3 to ≤ 7 kg: 100 mg once per day through the intensive PK sampling visit*, then 50 mg three times per week on Monday, Wednesday, and Friday through the Week 24 visit

*Intensive PK sampling will be performed at the Week 1 or Week 2 visit following receipt of at least 14 and no more than 17 BDQ daily doses, including any non-study BDQ doses taken prior to study entry.

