3.1 Primary Outcome Measures (evaluated through week 24)

- Termination from treatment due to a drug-related AE
- AEs of \geq grade 3 severity
- AEs of \geq grade 3 severity assessed by the Core Team to be at least possibly related to the study drug
- Absolute QTcF interval \geq 500msec
- Unstable dysrhythmias requiring hospitalization and treatment
- Death (grade 5 AE)

3.2 Secondary Outcome Measures (evaluated through Week 96 / 72 weeks post BDQ discontinuation)

- AEs of \geq grade 3 severity

- AEs of \geq grade 3 severity assessed by the Core Team to be at least possibly related to the study drug
- Absolute QTcF interval \geq 500msec
- Unstable dysrhythmias requiring hospitalization and treatment
- Death (grade 5 AE)

NOTE: For the outcome measures 3.1 and 3.2 above, for creatinine events under protocol Version 1.0, serum creatinine grading for the study analyses will be based on the absolute value only as per the DAIDS AE Grading Table (Corrected Version 2.1, dated July 2017) and not on percentage change from the participant's baseline value. This is consistent with creatinine grading requirements in protocol Version 2.0.

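### Does the SAP's Week 24 window, which runs to day 195, let events after the end of BDQ dosing into the on-treatment primary safety outcome?

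*SAP*

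**What the plan says.** The heading of SAP Section 3.1 begins "Primary Outcome Measures (evaluated through week 24"; no study day is attached. Section 4.1 describes the period for the whole primary analysis: "The primary safety analyses will focus on the 24-week time period during BDQ treatment". The excerpt of protocol Section 9.6.1 in Clarification Memorandum #1 opens in the same way. Section 4.1 later refers to "a primary evaluation of safety across the 24 weeks of study treatment". The dosing table in Section 2.1 has the maintenance dose given "on Monday, Wednesday, and Friday through the Week 24 visit".

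Section 4.2 introduces its assessment windows with "For all analyses, the relative weeks of visit date/specimen date/onset date/other dates". The Week 24 row has target day 168 and covers days 161 to 195; Week 32 starts on day 196.

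Section 4.3 adds an on-drug condition for two groups. For participants taken off treatment for reasons other than toxicity, "those who experienced a primary safety outcome measure while on study drug will be considered as safety failure for that outcome measure". Those off study before the Week 24 visit are not failures "unless this was experienced before they were off study and while on study drug". No equivalent sentence is written for completers.

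Sections 1.1 and 5 leave coding descriptions and detailed report content to the AIP, which is not among the supplied documents.

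**The concern.** Onset dates are named in the Section 4.2 rule, and the rule is said to hold for all analyses. Read literally, an adverse event starting on day 190 belongs to Week 24 and so falls within an outcome evaluated through week 24. For a participant whose last dose was on day 168, that event began 22 days after dosing ended.

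Two things would be at stake. The primary proportion would include off-drug time although Section 4.1 describes it as on-treatment. It would also mix two at-risk periods: early stoppers for non-toxicity reasons counted only on drug, and completers counted for up to several weeks more. Section 4.2 requires that "All dataset creation programs will be validated with double coding for the primary and secondary safety endpoints". That could reveal two programmers reading the text differently, but it would not tell them which reading was meant.

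**Working it through.** **The window.** Week 24 target: 24 × 7 = day 168. The midpoint between the Week 24 and Week 32 targets is (168 + 224)/2 = 196, so the last whole day before it is 195, which reproduces the table. The same pattern holds for most of the table: 11 of its 15 boundaries between adjacent windows lie at or within one day of the midpoint (10, 20, 35, 49, 69, 98, 126, 195, 252, 308 and 462, against 10, 20.5, 35, 49, 70, 98, 126, 196, 252, 308 and 462). A table built this way mainly assigns each assessment to its nearest scheduled visit. Its columns refer to assessments, and its last rows are named visits.

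**Off-drug days if the table were used to count events.** Days = 195 − day of last dose. Day 168 gives 27 (27/168 = 16% more observation time), day 182 gives 13 and day 195 gives 0. A last dose on day 161 would give 34, but that is an edge case. The supplied text gives no visit allowance, so the spread of last-dose days is unknown.

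**Effect on the proportion.** Assumptions: constant hazard that continues unchanged off drug; risk p to day 168 of 10%, 20% or 30%; last dose on day 168; 54 analysed (the planned evaluable number, since the size of the primary set is not fixed). Risk to day 195 = 1 − (1 − p)^(195/168).

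| p to day 168 | Risk to day 195 | Difference | × 54 | × 18 (one cohort) |
|---|---|---|---|---|
| 10% | 11.51% | 1.51 points | 0.82 | 0.27 |
| 20% | 22.82% | 2.82 points | 1.52 | 0.51 |
| 30% | 33.90% | 3.90 points | 2.11 | 0.70 |

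**Against precision.** The Clopper-Pearson 95% interval for 11/54 (20.4%) is 10.6% to 33.5%, a width of 22.9 points. The 2.82-point shift at 20% risk is about one eighth of that. For 5/18 the interval is 9.7% to 53.5%, a width of 43.8 points.

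**Which reading the SAP supports.**

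- Section 4.1 states a period for the primary analysis. Section 4.2 states how to label dates. Only the first says what is to be analysed.
- For completers, dosing lasts to the Week 24 visit, so counting through Week 24 and counting on drug nearly coincide. The on-drug condition in Section 4.3 is written for the groups in whom they separate.
- The table has an Early Discontinuation row reaching 14 days past the last dose, yet Section 4.3 counts non-toxicity early stoppers only on drug. For that group the window clearly does not define countable events.
- Section 1.1 starts the Primary Analysis Report from the last participant's Week 24 visit, and Section 4.1 from completion of the 24-week regimen. Neither waits for day 195.
- One of the six primary outcomes, termination of treatment for a drug-related event, cannot arise in a completer after the last dose.

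**The case for a change.** The strongest counter-argument is that the period of a primary outcome belongs in the SAP. Section 1.1 makes the SAP the place of agreement between team and statisticians and the basis for the posted primary safety results. A sentence that covers onset dates in all analyses is explicit, whereas the wording in Section 4.1 describes a period without dating its end. A single event is also visible in a cohort of 18, at 1/18 = 5.6 percentage points.

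Part of this stands. The supplied text gives no cut-off day for completers, and Section 4.2 would be read more easily if it separated visit labelling from event counting. The AIP may already hold the rule, but that cannot be confirmed here. Nor does Section 4.3 state a counting period for the other outcomes of participants who stop because of toxicity, so a cut-off for completers alone would not fully equalise at-risk time.

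It does not establish that off-drug events will be counted. That requires the general labelling rule to override the specific description of the primary period. The choice of end date is also open to fair disagreement. The Week 24 visit date keeps that visit's ECG and laboratory results. The last-dose date is strictly on-treatment. A short post-dose period could be defended too, since Section 2.2.2 plans BDQ concentrations after discontinuation.

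**Conclusion.** No change is needed. This is missing operational detail that analysts would fill sensibly: Section 4.1 sets an on-treatment period, dosing ends at the Week 24 visit, and the windows serve visit assignment. The exact end date for completers is the kind of coding detail the SAP assigns to the AIP.

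If the wider reading were adopted, the cost would be about 0.8 to 2.1 extra participants of 54, or 0.3 to 0.7 in a cohort of 18. Those figures assume a last dose on day 168, a 24-week risk of 10% to 30% and a constant hazard continuing off drug; a lower off-drug hazard or a later last dose would reduce them, and an earlier last dose would raise them. The primary safety results are descriptive proportions with exact intervals, and no hypothesis test or decision rule depends on them.

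Neither reading would hide an event. Section 4.1 requires listings of all events of grade 3 or higher, and Section 3.2 repeats five of the six primary outcomes through Week 96, so anything starting between days 169 and 195 is reported in any case.
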